	5.6.1	Primary estimand for the primary objective
	5.6.2	Handling of missing values not related to intercurrent event
	5.6.3	Supplementary analysis

List of abbreviations

AE	Adverse Event
AESI	Adverse Events of Special Interest
ALP	Alkaline phosphatase
ALT	Alanine aminotransferase/glutamic pyruvic transaminase/GPT
AST	Aspartate aminotransferase/glutamic oxaloacetic transaminase/GOT
ATC	Anatomical Therapeutic Chemical
BID	bis in diem/twice a day
BOR	Best Overall response
CBR	Clinical Benefit Rate
CI	Confidence Interval
CR	Complete Response
CSR	Clinical study report
CTCAE	Common Terminology Criteria for Adverse Event
DAR	Dose Administration Record
DOR	Duration of Response
ECG	Electrocardiogram
eCRF	Electronic Case Report Forms
eCRS	Electronic Case Retrieval Strategy
ECHO	Echocardiogram
EoT	End of Treatment
FAS	Full Analysis Set
HGG	High Grade Glioma
LGG	Low Grade Glioma
MedDRA	Medical Dictionary for Regulatory Activities
MRI	Magnetic resonance imaging
NMQ	Novartis MedDRA Query
ORR	Overall Response Rate
OS	Overall Survival
PD	Progressive Disease
PFS	Progression-Free Survival
PK	Pharmacokinetics
PR	Partial Response
PT	Preferred Term
QT	Q to T interval (ECG)
QTcF	QT interval corrected using Fridericia method
RANO	Response Assessment in Neuro-Oncology
SAE	Serious Adverse Event
SAP	Statistical Analysis Plan
SD	Stable Disease
SDS	Standard Deviation Score
SOC	System Organ Class
SMQ	Standardized MedDRA Query

Total bilirubin
Time To Response
Upper limit of normal
Unknown
White blood cells
World Health Organization

1 Introduction

This statistical analysis plan (SAP) describes all planned analyses for the High Grade Glioma (HGG) cohort of the final clinical study report (CSR) of study CDRB436G2201, a multi-center, global, single-arm, open-label, Phase II study conducted in children and adolescent patients with BRAF V600 mutation positive, (a) Low Grade Glioma (LGG), or (b) refractory or relapsed HGG after having received at least one previous standard therapy. This SAP will be used for the final analysis for the HGG cohort. All planned analyses for the LGG cohort are described in a separate SAP.

The content of this SAP is based on protocol CDRB436G2201 amendment version 05. All decisions regarding the final analysis, as defined in this SAP, have been made prior to the final database lock.

1.1 Study design

This study combines two pediatric glioma cohorts (HGG and LGG) into a single multi-center, open-label, phase II study.

The HGG cohort is a multi-center, single-arm, open-label, Phase II study conducted in children and adolescent patients with BRAF mutation positive, refractory or relapsed HGG tumors after having received at least one previous standard therapy. BRAF V600 mutation-positive tumor was assessed locally, or at a Novartis designated central reference laboratory if local BRAF V600 testing was unavailable. Approximately 40 patients will be enrolled to receive dabrafenib and trametinib.

The primary objective is to evaluate the antitumor activity of dabrafenib in combination with trametinib, as measured by the overall response rate (ORR) to study treatment by independent central review assessment using response assessment in neuro-oncology (RANO) criteria in the Full Analysis Set (FAS) population. ORR as assessed through investigator review, duration of response (DOR), time to response (TTR), progression-free survival (PFS), clinical benefit rate (CBR) assessed by investigator and independent central review, overall survival (OS), palatability, pharmacokinetics (PK), and the safety and tolerability profile of dabrafenib and trametinib are secondary endpoints.

Patients may continue to receive the assigned study treatment until disease progression by RANO criteria or loss of clinical benefit as determined by the investigator, unacceptable toxicity, start of a new anti-neoplastic therapy, discontinuation at the discretion of the investigator or patient/legal guardian, lost to follow-up, death, or study is terminated by the sponsor.

Patients who have disease progression by RANO criteria may continue study treatment if the investigator determines that patient has clear evidence of clinical benefit from study treatment, continuing study treatment may be in the best interest for the patient, and the patient/legal guardian is willing to continue on study treatment and sign the informed consent for treatment beyond progression. The decision to continue study treatment after progressive disease (PD) must be documented in the patient records and electronic case report forms (eCRF) after every tumor evaluation. In this case, the patient will continue assessments as defined in the study

Novartis	Confidential	Page 8
SAP Final Analysis HGG		CDRB436G2201

[Protocol Section 7]. An end of treatment visit will be performed when patients permanently discontinue study treatment.

Patients who discontinue the study treatment without disease progression by RANO criteria will continue tumor assessments as outlined in the study protocol section 7 until documented centrally confirmed disease progression by RANO criteria or death irrespective of start of new anti-neoplastic therapy.

Patients who discontinue study treatment and efficacy follow-up will enter a follow-up period during which survival will be collected every 3 months. During the survival follow-up, subsequent anti-neoplastic therapies initiated after study treatment discontinuation will be collected.

The final analysis will be performed when all patients in both cohorts have been followed for survival for at least 2 years from last patient first study treatment, except if consent is withdrawn, death, or patient is lost to follow-up or study discontinuation.

1.2 Study objectives and endpoints

A list of all study objectives and endpoints is given below. For the final CSR, not all study objectives will be reported, as they have already been analyzed in the primary analysis. This is documented in the corresponding SAP section for each objective.

Objective	Endpoint
Primary	
To evaluate the anti-tumor activity of dabrafenib in combination with trametinib, as measured by overall response rate (ORR) by central independent assessment using the RANO criteria.	ORR, proportion of patients with a best overall confirmed Complete Response (CR) or Partial Response (PR) by independent review assessment per Response Assessment in Neuro-Oncology (RANO) criteria.
Secondary	
 a) Evaluate ORR by investigator assessment b) Evaluate duration of response (DOR) by investigator and central independent review c) Evaluate progression free survival (PFS) by investigator and central independent review d) Evaluate time to response (TTR) by investigator and central independent review e) Evaluate clinical benefit rate (CBR) by investigator and central independent review e) Evaluate clinical benefit rate (CBR) by investigator and central independent review f) Evaluate overall survival (OS) g) Evaluate the safety and tolerability profile of dabrafenib in combination with trametinib in children and adolescents h) Evaluate the palatability of dabrafenib oral suspension and trametinib oral solution i) Characterize the pharmacokinetics of dabrafenib, its metabolites and trametinib in the study population 	 ORR by investigator assessment per RANO criteria DOR, calculated as the time from the date of the first documented confirmed response (CR or PR) to the first documented progression or death due to any cause, as assessed separately by investigator and central independent reviewer per RANO criteria. PFS, defined as time from first dose of study treatment to progression or death due to any cause, as assessed separately by central independent reviewer and investigator per RANO criteria

Objective	Endpoint
	4. TTR, calculated as the time from the start date of study treatment to first documented confirmed response CR or PR (which must be confirmed subsequently) as assessed separately by investigator and independent central reviewer per RANO criteria
	 CBR is the proportion of patients with a bes overall response of CR or PR, or an overall lesion response of SD which lasts for a minimum time duration of at least 24 weeks as assessed separately by investigator and central independent reviewer per RANO criteria.
	6. OS, defined as the time from first dose of
	 study treatment to death due to any cause 7. Incidence of adverse events and serious adverse events, changes in laboratory results, vital signs, ECG and ECHO
	8. Palatability questionnaire data
	 Plasma concentration-time profiles of dabrafenib, its metabolites and trametinib and PK parameters

2 Statistical methods

2.1 Data analysis general information

The final analysis will be performed by Novartis. SAS version 9.4 or later software will be used to perform all data analyses and to generate tables, figures and listings.

Data included in the analysis

A unique cut-off date will be determined for the final analysis, corresponding to the last patient last visit date on the study. The analysis cut-off date will be established at the end of the study when all patients in both cohorts have been followed-up for survival for at least 2 years from last patient first treatment, except if consent is withdrawn, death, or patient is lost to follow-up or study discontinuation.

All statistical analyses will be performed using all data collected in the database up to the data cut-off date. All data with an assessment date or event start date (e.g. vital sign assessment date or start date of an adverse event [AE]) prior to or on the cut-off date will be included in the analysis. Any data collected beyond the cut-off date will not be included in the analysis and will not be used for any derivations. Note that for the final analysis, the cut-off date will be defined such that no data are collected beyond the cut-off date, i.e. all collected data will be included in the analysis.

All events with start date before or on the cut-off date and not having a documented end date will be reported as 'ongoing'. This approach applies, in particular, to AE and concomitant medication records.

General analysis conventions

Pooling of centers: unless specified otherwise, data from all study centers will be pooled for the analysis. Due to expected small number of patients enrolled at centers, no center effect will be assessed.

Qualitative data (e.g., gender, race, etc.) will be summarized by frequency counts and percentages; a missing category will be included as applicable. Percentages will be calculated using the number of patients in the relevant population or subgroup as the denominator.

Quantitative data (e.g., age, body weight, etc.) will be summarized by appropriate descriptive statistics (i.e. n, mean, standard deviation, median, 25th-75th percentiles, minimum, and maximum).

2.1.1 General definitions

Investigational drug and study treatment

Study treatment will refer to dabrafenib and trametinib combination. *Study drug* will refer to each component of study treatment.

Date of first administration of study treatment

The date of first administration of study treatment is derived as the first date when a non-zero dose of any component of study treatment was administered as per the Dosage Administration

Novartis	Confidential	Page 11
SAP Final Analysis HGG		CDRB436G2201

eCRF. (Example: if first dose of dabrafenib is administered on 05-Jan-2015, and first dose of trametinib is administered on 03-Jan-2015, then the date of first administration of study treatment is on 03-Jan-2015). For the sake of simplicity, the date of first administration of study treatment will also be referred as *start of study treatment*.

Date of last administration of study treatment

The date of last administration of study treatment is derived as the last date when a non-zero dose of any component of study treatment was administered as per Dose Administration Record (DAR) eCRF (Example: if the last dabrafenib dose is administered on 15-Apr-2014, and the last dose of trametinib is administered on 17-Apr-2014, then the date of last administration of study treatment is on 17-Apr-2014).

Study day

The study day, describes the day of the event or assessment date, relative to the reference start date.

The study day is defined as:

- The date of the event (visit date, onset date of an event, assessment date etc.) reference start date + 1 if event is on or after the reference start date;
- The date of the event (visit date, onset date of an event, assessment date etc.) reference start date if event precedes the reference start date.

The reference date for all assessments (safety, efficacy, PK, performance status etc.) is the start of study treatment.

The study day will be displayed in the data listings. If an event starts before the reference start date, the study day displayed on the listing will be negative.

Time unit

A year length is defined as 365.25 days. A month length is 30.4375 days (365.25/12). If duration is reported in months, duration in days will be divided by 30.4375. If duration is reported in years, duration in days will be divided by 365.25.

Baseline

For safety and efficacy evaluations, the last available assessment on or before the date of start of study treatment is defined as the baseline assessment. In the rare case that time of assessment and time of treatment start is captured, the last available assessment before the treatment start date/time is used for baseline. If there is more than one record on the same day of screening the highest value would be considered as baseline. For laboratory data, if there is more than one record on the same day of screening, then records from central laboratory should take precedence over local laboratory records.

If patients have no value as defined above, the baseline result will be missing.

On-treatment assessment/event and observation periods

For safety reporting the overall observation period will be divided into three mutually exclusive segments:

- 1. *pre-treatment period*: from day of patient's informed consent to the day before first administration of study treatment
- 2. *on-treatment period*: from date of first administration of study treatment to 30 days after date of last actual administration of any study treatment (including start and stop date)
- 3. *post-treatment period*: starting at day 30+1 after last administration of study treatment.

Notes: if data on clock time is available in the clinical database (e.g. for time of blood/urine sample taken, electrocardiogram (ECG) performed, etc. and first study treatment administration), a more precise distinction between pre-treatment and on-treatment periods is encouraged to be used. If dates are incomplete in a way that clear assignment to pre-, on-, post-treatment period cannot be made, then the respective data will be assigned to the on-treatment period.

Safety summaries (tables, figures) include only data from the on-treatment period with the exception of baseline data which will also be summarized where appropriate (e.g. change from baseline summaries). In addition, a separate summary for death including on treatment and post treatment deaths will be provided. In particular, summary tables for AEs will summarize only on-treatment events with a start date during the on-treatment period (*treatment-emergent* AEs).

However, all safety data (including those from the post-treatment period) will be listed and those collected during the pre-treatment and post-treatment period will be flagged.

Windows for multiple assessments

In order to summarize Karnofsky/Lansky performance status, physical exam, vital signs, ECG, and laboratory data collected over time (including unscheduled visits), the assessments will be time slotted. Time windows will be defined for descriptive summary by visit. The following general rule will be applied in creating the assessment windows: if more than one assessment is done within the same time window, the assessment performed closest to the target date will be used. If two or more assessments within a time window are equidistant from the target date or on the same date, then the maximum will be used. For growth and ECG analysis, if two assessments within a time window are equidistant from the target date then the mean will be used. For laboratory data, if two assessments within a time window are equidistant from the target date or on the same date or on the same date, then records from central laboratory should take precedence over local laboratory records. Data from all assessments (scheduled and unscheduled), including multiple assessments, will be listed.

 Table 2-1
 Time windows for Karnofsky/Lansky performance status/Urinalysis

Time Window	Planned Visit Timing	Time Window Definition
On treatment		
Baseline (Week 1 Day 1)	On or before Study Day 1ª	≤ Study Day 1
Week 5 Day 1	Study Day 29	Study Days 27 – 31
Week 8 Day 1	Study Day 50	Study Days 43 – 57

Time Window	Planned Visit Timing	Time Window Definition
Every 8 weeks thereafter		
Week y=8+8*k	Study Day (8+8*k-1)*7+1	Study Day
(with k = 1, 2,, 6)		(8+8*k-1)*7+1-7 to
		(8+8*k-1)*7+1+7
Every 16 weeks thereafter		
Week y=56+16*k	Study Day (56+16*k-1)*7+1	Study Day
(with k = 1, 2,)		(56+16*k-1)*7+1-7 to
		(56+16*k-1)*7+1+7
End of treatment (EoT)		
EoT	Within 30 days after last dose	Earliest data available on or after EoT date up to and including 30 days after EoT
Post treatment ^b		
Post treatment follow-up 1	Post treatment study day 16*7	Post treatment Study Days 16*7 - 14 to 16*7 + 14
Post treatment follow-up k (with k = 2, 3,)	Post treatment study day 16*k*7	Post treatment study days 16*k*7 - 14 to 16*k*7 + 14

^bPost treatment study day 1=end of treatment date + 1 day

Table 2-2 Time windows for physical exam/vital signs/hematology/chemistry

Time Window	Planned Visit Timing	Time Window Definition
On treatment		
Baseline (Week 1 Day 1)	On or before Study Day 1 ^a	≤ Study Day 1
Week 2 Day 1	Study Day 8	Study Days 6 – 10
Week 3 Day 1	Study Day 15	Study Days 13 – 17
Week 4 Day 1	Study Day 22	Study Days 20 – 24
Week 5 Day 1	Study Day 29	Study Days 27 – 31
Week 8 Day 1	Study Day 50	Study Days 43 – 57
Every 8 weeks thereafter		
Week y=8+8*k	Study Day (8+8*k-1)*7+1	Study Day
(with k = 1, 2,, 6)		(8+8*k-1)*7+1-7 to
		(8+8*k-1)*7+1+7
Every 16 weeks thereafter		
Week y=56+16*k	Study Day (56+16*k-1)*7+1	Study Day
(with k = 1, 2, …)		(56+16*k-1)*7+1-7 to
		(56+16*k-1)*7+1+7
End of treatment (EoT)		
EoT	Within 30 days after last dose	Earliest data available on or

Time Window	Planned Visit Timing	Time Window Definition
		after EoT date up to and including 30 days after EoT
Post treatment ^b		
Post treatment follow-up 1	Post treatment study day 16*7	Post treatment Study Days 16*7 - 14 to 16*7 + 14
Post treatment follow-up k (with k = 2, 3,)	Post treatment study day 16*k*7 30	Post treatment study days 16*k*7 - 14 to 16*k*7 + 14

^aStudy Day 1 = start date of study treatment

^bPost treatment study day 1=end of treatment date + 1 day

Table 2-3 Time windows for ECG/Visual Acuity

Time Window	Planned Visit Timing	Time Window Definition
On treatment		
Baseline (Week 1 Day 1)	On or before Study Day 1 ^a	≤ Study Day 1
Week 5 Day 1	Study Day 29	Study Days 27 – 31
Week 16 Day 1	Study Day 106	Study Days 99 – 113
Week 32 Day 1	Study Day 218	Study Days 211 – 225
Week 48 Day 1	Study Day 330	Study Days 323 – 337
Week 72 Day 1	Study Day 498	Study Days 491 – 505
Every 16 weeks thereafter		
Week y=16+16*k	Study Day (16+16*k-1)*7+1	Study Day
(with k = 1, 2,)		(16+16*k-1)*7+1-7 to
		(16+16*k-1)*7+1+7
End of treatment (EoT)		
EoT	Within 30 days after last dose	Earliest data available on or
		after EoT date up to and
		including 30 days after EoT

For all analyses regarding abnormal assessments or analyses based on worst or best postbaseline value (laboratory, ECGs, vital signs, Karnofsky/Lansky performance status, echocardiogram (ECHO), ophthalmologic exam, dermatologic exam, etc.), all post-baseline values will be included (scheduled, unscheduled, repeat).

Last contact date

The last contact date will be derived for patients not known to have died at the analysis cut-off using the last complete date among the sources specified in Table 2-4.

Table 2-4	Last contact date	data sources
	Luot contact auto	

Source data	Conditions
Date of Randomization	No Condition
Last contact date/last date patient was known to be alive from Survival Follow-up page	Patient status is reported to be alive, lost to follow-up or unknown.
Start/End dates from further antineoplastic therapy	Non-missing medication/procedure term.
Start/End dates from drug administration record	Non-missing dose. Doses of 0 are allowed.
End of treatment date from end of treatment page	No condition.
Tumor (RANO) assessment date	Evaluation is marked as 'done'.
Laboratory dates	Sample collection marked as 'done'.
Vital signs date	At least one non-missing parameter value
Performance Status date	Non-missing performance status
Start/End dates of AE	Non-missing verbatim term

The last contact date is defined as the latest complete date from the above list on or before the data cut-off date. The cut-off date will NOT be used for last contact date, unless the patient was seen or contacted on that date. No date post cut-off date will be used. Completely imputed dates (e.g. the analysis cut-off date programmatically imputed to replace the missing end date of a DAR) will not be used to derive the last contact date. Partial date imputation is allowed for event (death)/censoring is coming from 'Survival information' eCRF. If the day is missing from the date of last contact, it will be imputed to the 15th day of the month and year of last contact only if derived from the survival page.

The last contact date will be used for censoring of patients in the analysis of OS.

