2.8.4 Other safety data

2.8.4.1 ECG and cardiac imaging data

ECG Data handling

In case the study requires ECG replicates at any assessment, the average of the ECG parameters at that assessment should be used in the analyses.

ECG Data analysis

Standard 12-lead ECGs including PR, QRS, QT, QTcF, and HR intervals will be obtained local for each patient during the study. ECG data will be read and interpreted locally.

The number and percentage of patients with notable ECG values will be presented:

- QT, QTcF
 - New value of > 450 and ≤ 480 ms
 - New value of > 480 and ≤ 500 ms
 - New value of > 500 ms
 - Increase from Baseline of $> 30 \text{ ms to} \le 60 \text{ms}$
 - Increase from Baseline of > 60 ms
- PR
 - Increase from baseline >25% and to a value >200 ms
 - New value of > 200 ms
- QRS
 - Increase from baseline >25% and to a value > 120 ms
 - New values of QRS > 120 ms

The normal range for HR is displayed in Table 2-11 Recommendation for normal heart rate per age group and gender. The number and percentage of patients with notable values will be presented.

Age group	1-<3 years	3-<5 years	5-<8 years	8-<12 years	12-<16 years	16-<20 years	20-<30 years
HR (bpm) Boys	(95, 155)	(75, 125)	(60, 115)	(55, 100)	(50, 100)	(50, 105)	(45, 95)
HR (bpm) Girls	(95, 180)	(80, 125)	(70, 115)	(60, 110)	(50, 100)	(45, 105)	(50, 100)

Table 2-11Recommendation for normal heart rate per age group and gender

Age should be age at assessment. Data shown as upper limit of normal, lower limit of normal for HR= heart rate. Ref.: adapted from Rijnbeek et al. 2001 and Rijnbeek et al. 2014

The summaries will include all ECG assessments performed no later than 30 days after the last date of study drug. A listing of all ECG assessments will be produced and notable values will be flagged. A separate listing of only the patients with notable ECG values may also be produced. In the listings, the assessments collected during the post-treatment period will be flagged.

The denominator to calculate percentages for each category is the number of patients with both a baseline and a post-baseline evaluation. A newly occurring post-baseline ECG notable value is defined as a post-baseline value that meets the criterion post-baseline but did not meet the criterion at baseline.

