In order to summarize Karnofsky/Lansky performance status, PK, physical exam, vital signs, ECG, laboratory data collected over time (including unscheduled visits), the assessments will be time slotted. Time windows will be defined for descriptive summary by visit. The following general rule will be applied in creating the assessment windows: if more than one assessment is done within the same time window, the assessment performed closest to the target date will be used. If 2 assessments within a time window are equidistant from the target date, then the worst case will be used. If multiple assessments on the same date then the worst case will be used. Data from all assessments (scheduled and unscheduled), including multiple assessments, will be listed.

 Table 2-1
 Time windows for Karnofsky/Lansky performance status/Urinalysis

Time Window	Planned Visit Timing	Time Window Definition
On treatment		
Baseline (Week 1 Day 1)	On or before Study Day 1*	≤ Study Day 1
Week 5 Day 1	Study Day 29	Study Days 27 – 31
Week 8 Day 1	Study Day 50	Study Days 43 – 57
Every 8 weeks thereafter		
Week y=8+8*k	Study Day (8+8*k-1)*7+1	Study Day
(with k = 1, 2,, 6)		(8+8*k-1)*7+1-7 to
		(8+8*k-1)*7+1+7
		Note: EOT data visit are included if obtained within 30 [^] days of last non-0 dose intake.
Every 16 weeks thereafter		
Week y=56+16*k	Study Day (56+16*k-1)*7+1	Study Day
(with k = 1, 2, …)		(56+16*k-1)*7+1-7 to
		(56+16*k-1)*7+1+7
		Note: EOT data visit are included if obtained within 30 [^] days of last non-0 dose intake.
End of treatment		
End of treatment	N.A.	Data collected under EOT visit if no data were collected at the EOT visit last available data obtained before EOT
Post treatment ^a		
Post treatment follow-up 1	Post treatment study day 16*7	Post treatment Study Days 16*7 - 14 to 16*7 + 14
Post treatment follow-up k (with k = 2, 3,)	Post treatment study day 16*k*7	Post treatment study days 16*k*7 - 14 to 16*k*7 + 14
	study treatment end of treatment date + 1 day e the time until total drug elimination	

Table 2-2Time windows for physical exam/vital signs/hematology/chemistry
--

Time Window	Planned Visit Timing	Time Window Definition
On treatment		
Baseline (Week 1 Day 1)	On or before Study Day 1*	≤ Study Day 1
Week 2 Day 1	Study Day 8	Study Days 6 – 10
Week 3 Day 1	Study Day 15	Study Days 13 – 17
Week 4 Day 1	Study Day 22	Study Days 20 – 24
Week 5 Day 1	Study Day 29	Study Days 27 – 31
Week 8 Day 1	Study Day 50	Study Days 43 – 57
Every 8 weeks thereafter		

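### In the final SAPs, parameters without a stated exception take the highest same-day record as baseline and the maximum at window ties, whichever direction is harmful

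*SAP*

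**What the plan says.** Final HGG SAP, section 2.1.1, Baseline, for safety and efficacy evaluations together: "If there is more than one record on the same day of screening the highest value would be considered as baseline". For laboratory data, "records from central laboratory should take precedence over local laboratory records". The final LGG SAP repeats both sentences in its safety baseline paragraph.

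Section 2.1.1, Windows for multiple assessments, opens with its scope: "In order to summarize Karnofsky/Lansky performance status, physical exam, vital signs, ECG, and laboratory data collected over time". If two or more assessments are "equidistant from the target date or on the same date, then the maximum will be used". Two exceptions follow. The first is "For growth and ECG analysis, if two assessments within a time window are equidistant from the target date then the mean will be used" (garbled in the LGG SAP, but evidently the same rule). The second gives central laboratory records precedence over local ones.

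Two later sections also bear on this. Section 2.8.4.1 says that, where ECG replicates are required, "the average of the ECG parameters at that assessment should be used in the analyses". Section 2.8.4.2 defines the vital-sign baseline as the most recent available value up to the first dose, without mentioning the highest.

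The September 2021 SAPs (HGG Amendment 2, LGG Amendment 1) had no highest-value baseline rule and settled window ties by direction of harm: "If multiple assessments on the same date then the worst case will be used".

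**The concern.** A tie rule for safety data should be neutral (the mean) or cautious (the worst value). Highest and maximum are neither, because their effect depends on the parameter. A highest baseline reduces every apparent rise, so it can understate a harmful increase in a change-from-baseline or shift table. A maximum at a window tie is cautious where high is harmful and favourable where low is harmful.

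At stake are some descriptive safety displays: vital-sign changes and shifts, logMAR worsening, laboratory shift tables, the liver signal for patients with abnormal baseline ALT or AST, and by-visit performance status. Each bias has a known direction and is easily avoided.

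**Working it through.** The plan states no figure on this point, so there is none to reproduce.

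**1. Which rule governs what (section 2.1.1 unless noted)**

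| Parameter | Same-day baseline records | Window tie |
|---|---|---|
| Vital signs | highest; 2.8.4.2 says most recent | maximum |
| Karnofsky/Lansky | highest | maximum |
| Laboratory, central and local | central | central |
| Laboratory, same source | highest (no exception) | maximum (no exception) |
| ECG, required replicates | average (2.8.4.1) | average within an assessment |
| ECG, other duplicates | highest | mean if equidistant; same date not named |
| Growth | highest | mean if equidistant; same date not named |

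Visual acuity also falls under the general baseline rule.

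**2. Direction at baseline.** Take two same-day records x1 ≤ x2. The highest exceeds the mean by x2 − (x1 + x2)/2 = (x2 − x1)/2, which is never negative. Every later change from baseline is therefore lower by (x2 − x1)/2 than with the mean.

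For patients with abnormal baseline ALT or AST, section 2.8.3 defines a liver signal partly by multiples of baseline:
- The 3 × baseline limit for ALT or AST rises by 3 × (x2 − x1)/2 = 1.5 (x2 − x1). This matters only while 3 × baseline is below the alternative limit of 8 × ULN.
- The 2 × baseline limit for bilirubin rises by 2 × (x2 − x1)/2 = x2 − x1. This matters only where it exceeds the accompanying 2 × ULN limit.

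**3. Size at baseline (illustration).** Assume independent normal records with within-day SD s. The documents give no s.
- Expected excess of the higher of two records over the true level: s/√π = 0.564 s. For s = 5, 10 and 15 units this is 2.8, 5.6 and 8.5 units. The mean of the two has no such bias.
- Share of patients with two baseline records who are classed as exceeding a cut-off for a rise, with one post-baseline value of the same SD (1,000,000 simulated patients per SD):

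| True rise relative to cut-off | Mean as baseline | Highest as baseline |
|---|---|---|
| equal | 50% | 33% |
| 0.5 SD above | 66% | 48% |
| 1 SD above | 79% | 63% |

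The first row also follows by symmetry. After subtracting the cut-off, the post-baseline value must be the largest of three exchangeable values, which has probability 1/3.

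**4. Direction at window ties.** For tied Karnofsky or Lansky scores of 70 and 90, the maximum is 90 and the worst case is 70. The by-visit category table (section 2.8.4.3) counts the patient under 90. The same happens with low pulse or low blood pressure in the by-visit summaries. In the LGG SAP, whose section 2.8.3 plans laboratory trends generally, it also happens with same-source laboratory values where low is harmful.

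**5. What the rules do not reach.** Section 2.1.1 includes all post-baseline values in abnormality and worst or best analyses, so window ties cannot change those. Worst CTC grade is reported whatever the baseline. The main liver categories are multiples of ULN. Worst-case performance status uses the lowest on-treatment score.

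**The case against.** Several wider readings are tempting, and the documents do not support them.

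- **The rules apply to every parameter.** They do not. Equidistant ECG and growth values are averaged, central laboratory records outrank local ones, and required ECG replicates are averaged.
- **The rules are anti-conservative throughout.** A highest baseline enlarges apparent falls, which is cautious for LVEF and performance status. A maximum at a tie is cautious where high is harmful.
- **By-visit neutrophils, platelets or haemoglobin are distorted in HGG.** The HGG SAP plans over-time laboratory displays for serum creatinine only, where high is harmful and the maximum is the cautious choice.
- **The effect can be sized on QTcF triplicates.** Section 2.8.4.1 averages required replicates, so that case is already covered. As the specific rule, it can be read together with the general baseline rule; what is missing is a sentence saying so.
- **ORR is affected because the HGG baseline rule names efficacy.** Section 5.5.4 takes response from the overall response reported by the independent reviewer or the investigator. No material effect is shown.
- **The change since September 2021 is itself an error.** It is not. It shows only that a direction-specific window rule had already been written for this trial.

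A fair practical objection is that same-day records cannot be ordered without clock times, which the SAP says are rarely captured. Some tie rule is therefore needed, and taking the last record would not work in general. That stands, and it is why the mean is preferable.

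The objections narrow the reach. They do not remove the bias for vital signs, logMAR, same-source laboratory values and performance status.

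**Conclusion.** The point holds for parameters without a stated exception, in both final SAPs. Where high is harmful, the baseline rule can only understate a rise. Where low is harmful, the window rule shows the better value in by-visit summaries. For logMAR, this assumes that the highest value is taken on the logMAR scale.

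For a patient with two same-day baseline records, the expected shift is 0.564 within-day SD under normality. Its effect on the tables depends on how often duplicates and exact ties occur, which the documents do not say. It is confined to descriptive safety displays, and all assessments are listed in any case. This is a minor correction, with no consequence for the primary result.

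**What to change.** In section 2.1.1 of both final SAPs:

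1. **Baseline.** For numeric parameters, use the mean of same-day records. For laboratory data, take central records first, then the mean of records from the same source. Use the last record only where clock time is captured. Karnofsky and Lansky scores come in multiples of 10, so state how a mean between two categories is assigned.
2. **Window ties.** Restore the direction-specific worst case. Keep the mean for ECG and growth, and extend it to assessments on the same date.
3. **Consistency.** State that the ECG replicate average (2.8.4.1) and the vital-sign baseline (2.8.4.2) operate within the section 2.1.1 rule, and align their wording.

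The cost is a few sentences and a direction-of-harm flag per parameter in programming. No new data are needed.
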